9.4 Frequency of data collection

Describe the frequency of data collection, including when safety data collection starts.

Safety data collection will begin at enrollment, as vital signs, serum pregnancy tests, and urine drug screens will be collected at that time, continue through the first medical appointment after enrollment in the study, and will be subsequently obtained at weekly intervals thereafter.

9.5 Individuals reviewing the data

Identify the individuals who will review the data. The plan might include establishing a data and safety monitoring committee and a plan for reporting data monitoring committee findings to the IRB and the sponsor.

The PI and study coordinator will review the safety data at weekly intervals with the assistance of the Data Management Unit at Penn State College of Medicine. Any adverse events deemed to be the result of study participation and not the result of routine eating disorder care will be reported to the IRB as well as the study sponsor.

9.6 Frequency of review of cumulative data

Describe the frequency or periodicity of review of cumulative data.

The PI and study coordinator will review the safety data at weekly intervals with the assistance of the Data Management Unit at Penn State College of Medicine. Any adverse events deemed to be the result of study participation and not the result of routine eating disorder care will be reported to the IRB as well as the study sponsor.

9.7 Statistical tests

Describe the statistical tests for analyzing the safety data to determine whether harms are occurring.

No statistical tests for analyzing safety data are scheduled for this trial.

9.8 Suspension of research

Describe any conditions that trigger an immediate suspension of research.

Monitoring for safety of the study article will be completed in accordance with Federal Food and Drug Administration requirements for surveillance of drug-induced liver injury (DILI), in accordance with Hy's law.

The study will be stopped early in the event of certain specific conditions that are more likely to be due to study intervention than to the disease itself. Several possible adverse effects of this medication can also be common features of eating disorder or eating disorder treatment itself, including worsening depression, self-injurious behavior, and suicide attempt ^{7,10,11,17,26–29}. The following circumstances would trigger immediate suspension of this study with evaluation of safety data and profile:

- Death of a study participant
- Psychiatric hospitalization for suicidal ideation in any two study participants within a six month window
- Two participants experiencing elevation of AST *or* ALT more than three times the upper limit of normal for age during the course of the study.
- AST or ALT levels elevated more than five times the upper limit of normal in any participant at any time.
- One participant with elevated serum total bilirubin to more than twice the upper limit of normal
 for age with evidence of pure hepatocellular injury (that is, no evidence of obstruction,
 malignancy, genetic disease, other medication effects, viral or bacterial infection) and AST or
 ALT elevation greater than three times the upper limit of normal for age.
- New diagnosis of liver failure of any participant
- Any other serious medical or psychiatric condition felt to be potentially related to the study article.

Any suspected case of drug-induced liver injury will be reported to the Food and Drug Administration using the specified information provided in the FDA's document, *Guidance for Industry Drug-Induced Liver Injury: Premarketing Clinical Evaluation*.

Should any participant demonstrate elevation of AST/ALT above the upper limit of normal for age, the study article will be discontinued. AST and ALT measures will be obtained twice weekly until they have normalized. More complete history will be obtained, specifically with respect to medications, supplements, recreational drug use history, travel, and chemical exposure. Participants with elevation of AST and ALT will also be evaluated for acute viral hepatitis types A, B, C, D, and E; autoimmune hepatitis, alcoholic hepatitis, non-alcoholic steatohepatitis, biliary tract disease, and hypoxic/ischemic hepatopathy. The liver's function will be assessed directly via measurement of direct bilirubin and nternational normalised ratio (INR).

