3.2 Exclusion Criteria

Create a numbered list of the exclusion criteria that define who will be excluded in your study.

- Diagnosis of intellectual disability
- History of known genetic or neurologic disease
- Need for treatment with opioid painkillers
- Weight <25kg
- Inability to swallow pills
- Lack of proficiency in written or spoken English
- Urine drug screen positive for opioids at enrollment
- Positive serum pregnancy test at enrollment
- Lactation
- Elevation of three times the upper limit of normal for age in either alanine aminotransferase (ALT) or asparagine aminotransferase (AST).
- High risk of suicide at enrollment on Columbia Suicide Severity Rating Scale (C-SSRS, for participants age 18)²⁰ or Ask Suicide Screening Questions (ASQ, participants age 13 to 17)²¹
- Current Naltrexone use

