3.3 Early Withdrawal of Subjects

3.3.1 Criteria for removal from study

Insert subject withdrawal criteria (e.g., safety reasons, failure of subject to adhere to protocol requirements, subject consent withdrawal, disease progression, etc.).

- New need for medical hospitalization for malnutrition or eating disorder
- Need for escalation of level of care for eating disorder, that is, requirement for inpatient or residential-level eating disorder care
- New need for opioid painkillers
- Subject consent withdrawal
- Inability to adhere to protocol requirements
- New diagnosis of pregnancy
- New elevation of three times the upper limit of normal for age in either alanine aminotransferase (ALT) or asparagine aminotransferase (AST).

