3.3.2 Follow-up for withdrawn subjects

Describe when and how to withdraw subjects from the study; the type and timing of the data to be collected for withdrawal of subjects; whether and how subjects are to be replaced; the follow-up for subjects withdrawn from investigational treatment.

- Patients who are withdrawn from the study will continue with their routine eating disorder
 care at whatever level of care is clinically appropriate for them at that time; that is, they will
 continue with routine care. Data generated from their participation in this study will be used
 to the point of their withdrawal. Specific study subjects do not require replacement.
- Patients who screen positive for opioid substances at enrollment will be provided with a referral for substance use disorder treatment.
- Patients who screen positive for pregnancy will be referred for pregnancy options counseling.

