6.2.1.2 Plan to destroy identifiers or a justification for retaining identifiers

Describe the plan to destroy the identifiers at the earliest opportunity consistent with the conduct of the research. Include when and how identifiers will be destroyed. If identifiers will be retained, provide the legal, health or research justification for retaining the identifiers.

All data will be maintained in RedCAP, and will be accessible only to study members. A key linking study participants to study data will be kept for the duration that the study data are kept, and all research data will be retained per FDA regulation and institutional policy. Data maintained in PennState Health drives will be destroyed in accordance with current data management protocols at our institution and paper records will be securely shredded and incinerated.

6.2.2 Explanation for why the research could not practicably be conducted without access to and use of PHI

Provide an explanation for why the research could not practicably be conducted without access to and use of PHI.

Much of the outcomes to be studied here, including weight restoration, length of time in care, or worsening of depression, are assessed on a regular basis as a part of routine clinical care. Because participants in this study will otherwise be undergoing routine care in PHP, access to PHI would reduce need for duplicate visits for study purposes only and should increase study retention. Additionally, certain inclusion and exclusion criteria, such as lab results, will be available in PHI and help determine participant eligibility.

6.2.3 Explanation for why the research could not practicably be conducted without the waiver or alteration of authorization

Provide an explanation for why the research could not practicably be conducted without the waiver or alternation of authorization.

Because participation in this study requires negative urine drug screen and normal bloodwork prior to enrollment, without being able to evaluate PHI prior to enrollment we will not be able to determine who is eligible without duplicating studies and potentially exposing the patient to excessive risk and pain in the form of duplicate lab studies and blood draws.

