7.1 Study Design

Describe and explain the study design.

This is a double-blind, randomized, placebo-controlled study. We have developed the following schedule of events. All events with a superscript $^{\circ}$ are for study purposes only and are not part of the standard of care:

	Pre-Enrollment Screening: Medical	Enrollment	Week 1	Week 2	Week 3	Week 4	Week 5	Week 6 (end of treatment	Week 8-9 (post- treatment)	Six Months
Intervention								_	>	
Initial Medical Assessment	Х									
Subsequent Medical Assessment, including comprehensive review of systems			x		x		x		х	х
Initial Psychiatry Assessment	X									
Subsequent Psychiatric Assessment, including suicidal ideation			х	х	х	х	х	х	х	х
Discussion of risks and benefits, inclusion and exclusion criteria ^o		х								
Consent/Assent ^o		Х								
\$25 Greenphire Clincardo		Х								х
Urine Drug Screen ^o		Х								
Serum Pregnancy Test (female participants)°		х								
Urine Pregnancy Test (female participants)°					х			х		
Administer Study Article ^o			Х	Х	х	Х	Х	х		
EKG	X									
AST	X				Xº			Xº		
ALT	Х				χ°			Xo		
Total Bilirubin	Х				Xº			Xº		
Direct bilirubin	Х				Xº			Xº		
Heart Rate	Х		Х	Х	Х	Х	Х	Х	Х	Х
BMI	X		Х	Х	Х	Х	Х	X	Х	Х
Height	X		Х	X	X	X	Х	X	X	Х
Weight	X		X	X	X	X	X	X	X	X
Blood Pressure	X		X	X	X	X	X	X	X	X
Temperature Adverse event monitoring ^o	Х		X	x	x	x	x	x	X	X
Suicidal Ideation Screening (ASQ			^	^	^	^	^			
for age <17or C-SSRS for age 18+)		х	Х	Х	х	Х	Х	х	Х	Х
ED-15		Х	х		х			Х	X	х
EDE-Q		Х	х		х			Х	X	Х
ABUSI°		Х	Х		х			Х	Х	Х
GAD-7		Х	х		х			Х	Х	Х
PHQ-9		Х	Х		Х			Х	X	Х
BIS/BAS°		Х	Х		Х			Х	Х	Х

Note: Medical assessments may occur in weeks 1,3 etc or 2,4 etc depending on standard of care for that patient. As long as patients are seen within a 14 day interval (2 week timeframe), the exact week intervals (1,3 or 2,4) may vary. Additionally, the 6 month follow up appointment may take place any time between 5-7 months after study enrollment ends.

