REDCap, will be used to store the surveys. Participants will be sent the link to the battery of surveys via email at the designated times listed above. The link will redirect them to the programmed surveys in REDCap. Their responses will be stored in REDCap until data is exported and stored on the secure file server (hersheymed.net/files). Only authorized study personnel will have access to the REDCap surveys and folder access on the secure network.

At initial contact with the eating disorders clinic, all patients receive an initial battery of laboratory tests as a part of the standard of care for eating disorder. These tests include liver function assays and transaminase levels. Further information about liver function test and monitoring for drug-induced liver injury is outlined in section 9.0.

7.1.1 Enrollment.

Provide a description of what procedures will be performed on visit 1 or day 1 or pre-test in order of how these will be done. If your study only involves one session or visit, use this section only and indicate 7.2.2 as not applicable.

As discussed above, patients can be enrolled at either their initial medical or initial psychiatric appointments for participation in the appropriate PHP for eating disorder.Per Joint Commission regulations of partial hospitalization programs for any psychiatric diagnosis, a complete blood count, blood chemistry, liver function test, urinalysis, and electrocardiogram must be obtained at enrollment and other studies at the program's discretion. If all necessary bloodwork, EKG, and urine studies have been obtained within the last two weeks, these results will be tracked down, recorded into the medical record, and any necessary and routine studies that have not been completed prior to this appointment will be completed at enrollment.

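### The AST/ALT entry limit (3x ULN) admits participants whom the stop rule (any value above ULN, no baseline exception) takes off study article at week 3

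*Combined protocol and SAP*

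**What the plan says.** Four parts of the protocol set a liver-enzyme threshold for the individual participant.

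- **Entry, section 3.2.** The only liver exclusion is "Elevation of three times the upper limit of normal for age in either alanine aminotransferase (ALT) or asparagine aminotransferase (AST"). Nothing in 3.1 or 3.2 covers a value above ULN but below three times ULN.
- **Stopping study article, sections 9.8 and 18.7 (same words in both).** "Should any participant demonstrate elevation of AST/ALT above the upper limit of normal for age, the study article will be discontinued". Then: "AST and ALT measures will be obtained twice weekly until they have normalized". Further history is taken, and a list of hepatitis and other liver causes is to be investigated where AST and ALT are elevated.
- **Removal from the study, section 3.3.1.** "New elevation of three times the upper limit of normal for age in either alanine aminotransferase (ALT) or asparagine aminotransferase (AST").
- **Privacy-waiver rationale, section 6.2.3.** "participation in this study requires negative urine drug screen and normal bloodwork prior to enrollment".

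The schedule in 7.1 puts baseline AST and ALT under "Pre-Enrollment Screening: Medical" and repeats them as study tests at weeks 3 and 6. Section 7.1.1 says that "a complete blood count, blood chemistry, liver function test, urinalysis, and electrocardiogram must be obtained at enrollment".

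**The concern.** The entry rule and the stop rule do not describe the same population. A person at, say, 2x ULN is eligible under 3.2 and already meets the condition for stopping under 9.8 and 18.7. The removal criterion in 3.3.1 is limited to a *new* elevation; the stop rule is not. Section 6.2.3 adds a third standard, under which that person would not have been enrolled at all.

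At stake is what happens when staff follow the text. An eligible participant with a stable, pre-existing value is taken off study article part-way through, in either arm, for a reason unrelated to the drug. Repeat blood tests follow, and a value that predates dosing may enter the safety record of a trial in which raised transaminases are a listed drug risk (section 10.0).

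**Working it through.** The plan gives no figure to reproduce on this point. The check sets the rules side by side and follows one participant through them.

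**Thresholds**

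| Action | AST/ALT level | Limited to new elevation? | Section |
|---|---|---|---|
| Exclude at entry | 3x ULN | Not applicable | 3.2 |
| Stop study article | above 1x ULN | No | 9.8, 18.7 |
| Remove from study | 3x ULN | Yes | 3.3.1 |
| Stated entry condition | normal | Not applicable | 6.2.3 |

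The window above 1x and below 3x ULN is open at entry under 3.2, closed under 6.2.3, and a reason to stop under 9.8 and 18.7.

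**A participant who enters in that window**

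1. *Doses.* Six weeks of daily dosing (7.3.2) is 6 × 7 = 42 doses. If the value is still above ULN at week 3, article stops after about 3 × 7 = 21. If it is normal at weeks 3 and 6, all 42 doses are taken and the rule never applies.
2. *Retests.* Twice-weekly testing from week 3 to week 6 is 3 × 2 = 6 draws; the last can double as the week-6 test. At the 4 ml per hepatic draw used in 9.1 (an assumption for retests), 6 × 4 = 24 ml. That alone exceeds the whole-study expectation in 9.1 of 16 ml (male) or 18 ml (female). Testing ends only when values become normal, so for a stable value the text sets no end at week 6.
3. *Further evaluation.* The hepatitis and related work-up is worded for elevation of AST *and* ALT. It clearly applies when both are raised; read literally, an isolated elevation does not trigger it.
4. *Adverse event record.* Section 18.2 classifies a test finding as an adverse event if it changes dosing or calls for additional diagnostic evaluation, with no baseline exception. Section 18.3 has the investigator decide whether the finding should be so classified, and whether it is related. The value may therefore be recorded, but need not be.

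**Number affected.** The documents give no share of enrollees at 1–3x ULN. For illustration, with N = 60 (8.1) and an assumed share p:

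- Expected number = 60p: 60 × 0.01 = 0.6; 60 × 0.05 = 3.0.
- Chance of at least one = 1 − (1 − p)^60: 1 − 0.99^60 ≈ 0.45; 1 − 0.95^60 ≈ 0.95.

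**Timing of the baseline result.** Section 7.3.3 randomises at enrolment. For participants enrolling at the psychiatry appointment, 7.1.1 describes labs as usually drawn at the first medical visit within the first seven days of programming. Section 7.2 makes supply of study article follow the urine drug screen and consent, and does not mention the liver result. On that route a pre-existing elevation could first be seen after dosing has started, when it can no longer be told from a new one.

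**The case against.** The strongest reply is that entry and treatment thresholds may properly differ. Stopping for a value still raised on a drug with a known liver signal is a cautious clinical choice, and someone whose value normalises by week 3 loses nothing. This stands as a defence of a strict stop rule. It does not explain admitting people who already meet that rule.

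A second reply is that 6.2.3 shows the intent: only people with normal bloodwork should enter, and 5.2.2 asks for all criteria to be checked before enrolment. That is plausible, and would make this a drafting slip in 3.2. But 6.2.3 is a privacy-waiver rationale, and staff screen from 3.1 and 3.2, where the condition does not appear.

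Several stronger readings are tempting, and the documents do not support them:

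- *That the participant must stop at baseline, with no doses taken.* Discontinuing presupposes that article was started, and the rule sits within text on the safety of study article. The week-3 test is the sound trigger.
- *That the stop rule conflicts with the removal rule.* Stopping article above 1x ULN and removing the participant at a new 3x ULN can be read as tiers.
- *That liver injury would be missed.* The stop rule is the more conservative one.
- *That primary-outcome data would be lost.* Section 3.3.2 uses withdrawn participants' data "to the point of their withdrawal. Specific study subjects do not require replacement", but 3.3.1 does not list stopping article below 3x ULN as a ground for removal.

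On blood volume, 9.1 states an expectation, and a genuinely new elevation would need the same follow-up. The volume shows only what would be spent on a value that predates the drug.

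**Conclusion.** The inconsistency is real and rests on the text alone. Section 3.2 admits AST/ALT between 1x and 3x ULN, 9.8 and 18.7 stop study article for any value above ULN without regard to baseline, and 6.2.3 says bloodwork must be normal. An eligible participant whose value persists stops at week 3 after about half of the planned doses and is retested twice a week until normal. The wider evaluation follows if both enzymes are raised, and the adverse event entry depends on the investigator's determination.

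The text comparison is certain; the size is not. The number affected may be zero or a few of 60: the 1% to 5% range is an assumption, as is 4 ml per retest. The point concerns a rule that misfires when followed. It should be fixed because eligibility and drug-stopping rules ought to agree before staff apply them, and because the repair is cheap.

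**What to change.** **Preferred.** Change 3.2 to exclude AST or ALT above ULN for age. This matches 6.2.3 and leaves the stop rule in 9.8 and 18.7 as it is. Add to 7.1.1, 7.2 and 7.3.3 that the liver function result already collected at enrolment is reviewed before randomisation and before the first dose.

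*Cost.* No new test or visit. There would be a few screen failures: 0.6 to 3 per 60 otherwise eligible participants at the assumed 1% to 5%, more if the share is higher. On the psychiatry route, where labs may come during the first week of programming, enrolment steps are reordered and the first dose may be delayed slightly relative to the program.

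**Alternative.** If the sponsor prefers to keep 3.2, the stop rule for participants with a raised baseline must name a defined multiple of the baseline value, capped at the 3x ULN removal threshold. A bare reference to a new elevation would leave staff without a trigger between baseline and 3x ULN. Section 6.2.3 must then be corrected. *Cost.* A somewhat less strict stop rule for these participants. The choice between the two is clinical.

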10.0 Risks

List the reasonably foreseeable risks, discomforts, hazards, or inconveniences to the subjects related the subjects' participation in the research. Include as may be useful for the IRB's consideration, a description of the probability, magnitude, duration and reversibility of the risks. Consider all types of risk including physical, psychological, social, legal, and economic risks. Note: Loss of confidentiality is a potential risk when conducting human subject research.

- If applicable, indicate which procedures may have risks to the subjects that are currently unforeseeable.
- If applicable, indicate which procedures may have risks to an embryo or fetus should the subject be or become pregnant.
- If applicable, describe risks to others who are not subjects.

Risks associated with taking oral naltrexone:

- elevated transaminases
- depression and mood changes
- abdominal pain
- nausea
- headache

Additional clinical risks that could be associated with taking Oral Naltrexone:

- Some pediatric autism literature describes low appetite or occasionally worsening of self-injurious behavior while on naltrexone^{8,11,22,22–25,27}. There can also be worsening depression according to the FDA label⁷. These adverse effects are occasionally seen with PHP for eating disorder itself, and therefore we monitor for them frequently as a part of the standard of care. Should the subject or the subject's parent wish to withdraw from the study due to these effects, they are free to do so. If these adverse effects are felt to be related more to the natural history of eating disorder and not to study intervention; or the severity is minor to moderate; the subject may continue to participate in the study if desired. If the effect is severe the subject will be withdrawn.
- Oral naltrexone is a pregnancy category C medication⁷, where there are animal studies that may indicate
 harm to the fetus but no specific human studies on this topic. For this reason, we will test for pregnancy
 in allbirth-assigned females at enrollment using a serum pregnancy screen, and every three weeks
 throughout the study using a urine pregnancy screen. The majority of patients enrolled in child PHP
 have not yet had coitarche, though in adult PHP a history of sexual activity is more common.

Other risks of participation include:

- Loss of confidentiality
- Risk of randomization
- Risk of incidental findings
 Anxiety from completing questionnaires

